Appendix I Important Protocol Deviations (Identified by Medical Review or Programmed)

Inclusion and exclusion criteria are referred according to Protocol version 11.0 dated 17-May-2017

| | Category of Protocol Deviation | Description of Protocol Deviation | Deviation Code | Clinically Important | Protocol Section | Proposed check / comment |
|--|--------------------------------|--|----------------|----------------------|------------------|--------------------------|
| Inclusion criteria: | | | | | | |
| For the subject to be eligible for inclusion, each criterion must be checked 'YES': | | | | | | |
| Signed written informed consent. | Informed Consent Criteria | Subject did not meet inclusion criterion 1. | PDEV01 | | Section 5.3.1 | Medical review required |
| Male or female subjects aged >=18 years | Eligibility and Entry Criteria | Subject did not meet inclusion criterion 2. | PDEV02 | | Section 5.3.1 | Medical review required |
| Histologically proven MCC | Eligibility and Entry Criteria | Subject did not meet inclusion criterion 3. | PDEV03 | Yes | Section 5.3.1 | Medical review required |
| Subjects must not have received any prior systemic treatment for metastatic MCC. Prior chemotherapy treatment in the adjuvant setting (no clinically detectable disease; no metastatic disease) is allowable if the end of treatment occurred at least 6 months prior to study start | Eligibility and Entry Criteria | Subject did not meet inclusion criterion 3d. | PDEV18 | Yes | Section 5.3.1 | Medical review required |
| Disease must be measurable with at least 1 unidimensional measurable lesion by RECIST 1.1 (including skin lesions) | Eligibility and Entry Criteria | Subject did not meet inclusion criterion 7. | PDEV04 | Yes | Section 5.3.1 | Medical review required |
| Effective contraception for both male and female subjects if the risk of conception exists | Eligibility and Entry Criteria | Subject did not meet inclusion criterion 11. | PDEV05 | | Section 5.3.1 | Medical review required |

| | Category of Protocol Deviation | Description of Protocol Deviation | Deviation Code | Clinically Important | Protocol Section | Proposed check / comment |
|--|--------------------------------|-------------------------------------|----------------|----------------------|------------------|--------------------------|
| Exclusion criteria: | | | | | | |
| For the subject to be eligible for inclusion, each criterion must be checked 'NO': | | | | | | |
| Concurrent treatment with a non-permitted drug | Eligibility and Entry Criteria | Subject met exclusion criterion 2. | PDEV06 | | Section 5.3.2 | Medical review required |
| Prior therapy with any antibody/drug targeting T cell co-regulatory proteins | Eligibility and Entry Criteria | Subject met exclusion criterion 3. | PDEV07 | Yes | Section 5.3.2 | Medical review required |
| Concurrent anti-cancer treatment (for example, cytoreductive therapy, radiotherapy [with the exception of palliative bone-directed radiotherapy, or radiotherapy administered to non-target superficial skin lesions], immune therapy, or cytokine therapy except for erythropoietin) | Eligibility and Entry Criteria | Subject met exclusion criterion 4. | PDEV08 | | Section 5.3.2 | Medical review required |
| Subjects with active central nervous system (CNS) metastases are excluded. Subjects with a history of treated CNS metastases (by surgery or radiation therapy) are not eligible unless they have fully recovered from treatment, demonstrated no progression for at least 2 months, and do not require continued steroid therapy | Eligibility and Entry Criteria | Subject met exclusion criterion 7. | PDEV19 | Yes | Section 5.3.2 | Medical review required |
| Previous malignant disease (other than MCC) within the last 5 years with the exception of basal or squamous cell carcinoma of the skin or cervical carcinoma in situ | Eligibility and Entry Criteria | Subject met exclusion criterion 8. | PDEV09 | | Section 5.3.2 | Medical review required |
| Pregnancy or lactation | Eligibility and Entry Criteria | Subject met exclusion criterion 14. | PDEV10 | | Section 5.3.2 | Medical review required |

| | Category of Protocol Deviation | Description of Protocol Deviation | Deviation Code | Clinically Important | Protocol Section | Proposed check / comment |
|---|--------------------------------|---|----------------|----------------------|-------------------------|--|
| Prohibited Medication Criteria | | | | | | |
| Non-permitted concomitant medication during the study | Prohibited Medications | Subject took Immunotherapy, immunosuppressive drugs (that is, chemotherapy or systemic corticosteroids except for short-term treatment of allergic reactions or for the treatment of irAEs), or other experimental pharmaceutical products. | PDEV11 | | Section 6.5.2 | Medical review required |
| Other criteria | | | | | | |
| Subjects that developed withdrawal criteria whilst on the study but were not withdrawn; | Other Criteria | Subject became pregnant, but continued on the study. | PDEV12 | | Section 5.5.2 | |
| Subjects who developed withdrawal criteria whilst on the study but were not withdrawn; | Other Criteria | Subjects received treatment despite confirmed progression and significant clinical deterioration. Subjects had ECOG \geq 3, did not resolved to \leq 2 by day 14 of next cycle, and continued on the study. | PDEV13 | | Section 5.5.2 and 5.5.3 | Medical review required |
| Subjects who developed withdrawal criteria whilst on the study but were not withdrawn; | Other Criteria | Subject developed grade 4 ADR, but continued on the study. | PDEV14 | | Section 5.5.2 and 5.5.3 | Medical review required |
| Subjects who developed withdrawal criteria whilst on the study but were not withdrawn; | Other Criteria | Subject developed grade 3 ADR, but continued on the study. | PDEV15 | | Section 5.1.4.2 | Medical review required |
| Subjects dosing error (\geq +/- 10 % assigned dose) | Other | Dosing error | PDEV16 | | Section 6.2 | List if relative dose intensity \geq 1.10 or \leq 0.90 |
| Subjects on avelumab treatment did not receive premedication | IP compliance | Subjects on avelumab treatment did not take mandatory premedication | PDEV17 | | Section 6.2 | Medical review required |

MSB0010718C MSB0010718C in Merkel Cell Carcinoma
EMR100070-003 Part B

| | Category of Protocol Deviation | Description of Protocol Deviation | Deviation Code | Clinically Important | Protocol Section | Proposed check / comment |
|---|---------------------------------------|--|-----------------------|-----------------------------|-------------------------|---------------------------------|
| Any other protocol deviation which is deemed to be significant but has not been pre-specified in this table | any | any | PDEV99 | | NA | Medical review required |

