5.3.2 Exclusion Criteria

Subjects are not eligible for this trial if they fulfill any of the following exclusion criteria:

1. Participation in another interventional clinical trial within the past 30 days (participation in observational studies are permitted)
2. Concurrent treatment with a nonpermitted drug
3. Prior therapy with any antibody/drug targeting T-cell coregulatory proteins (immune checkpoints) such as anti-PD-1, anti-PD-L1, or anticytotoxic T-lymphocyte antigen-4 (CTLA-4) antibody; for Part B, the Investigator must consult with the Medical Monitor and consider other co-regulatory targets such as 4-1BB
4. Concurrent anticancer treatment (for example, cytoreductive therapy, radiotherapy [with the exception of palliative bone-directed radiotherapy, or radiotherapy administered on non-target superficial lesions], immune therapy, or cytokine therapy except for erythropoietin). Radiotherapy administered to superficial lesions is not allowed if such lesions are considered target lesions in the efficacy evaluation or may influence the efficacy evaluation of the investigational agent
5. Major surgery for any reason, except diagnostic biopsy, within 4 weeks and/or if the subject has not fully recovered from the surgery within 4 weeks
6. Concurrent systemic therapy with steroids or other immunosuppressive agents, or use of any investigational drug within 28 days before the start of trial treatment. Short-term administration of systemic steroids (that is, for allergic reactions or the management of irAEs) is allowed while on study. Also, subjects requiring hormone replacement with corticosteroids for adrenal insufficiency are eligible if the steroids are administered only for the purpose of hormonal replacement and at doses ≤ 10 mg or equivalent prednisone per day. Note: Subjects receiving bisphosphonate or denosumab are eligible
7. Subjects with active central nervous system (CNS) metastases are excluded. Subjects with a history of treated CNS metastases (by surgery or radiation therapy) are not eligible unless they have fully recovered from treatment, demonstrated no progression for at least 2 months, and do not require continued steroid therapy
8. For Part A: Previous malignant disease (other than MCC) within the last 5 years with the exception of basal or squamous cell carcinoma of the skin or cervical carcinoma in situ

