8.4 Analysis Sets

The primary analysis population for all analyses of efficacy, safety, and health-related quality of life is the Safety population.

The Safety population will include all subjects who received at least 1 dose of trial treatment.

The Per-Protocol (PP) population will be the subset of the Safety population that is compliant with the protocol and excludes subjects with protocol violations. The protocol violation criteria will be outlined in the SAP. The per-protocol population will be used for additional sensitivity analyses for the primary and secondary efficacy endpoints.

Analysis of efficacy variables may also be performed on subgroups of interest and will be outlined in the Statistical Analysis Plan.

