8.3 Final Analysis

All planned analyses outlined in this SAP will be performed for the primary analysis. A partial database lock will be performed for the interim and primary analyses. The full DB lock will take place 5 years after the last subject receives the last dose of avelumab, or when the last subject dies, whichever occurs first.

In addition, no database can be locked until this SAP has been approved.

Subjects follow-up for progression and survival will continue until 5 years after the last subject receives the last dose of avelumab, or when the last subject dies, whichever occurs first. Under some circumstances, subjects may not be followed for 5 years for survival in this study, for example, subjects may be offered to enroll into a rollover study, or the Sponsor may terminate the study early.

9 Changes to the Planned Analyses in the Clinical Trial Protocol

The statistical methods as described in the protocol for Part B of this study were adopted.

10 Analysis Sets

Screening Analysis Set

The screening analysis set includes all subjects who signed the informed consent.

Full Analysis Set / Safety Analysis Set

Full analysis set (FAS) / Safety analysis set will include all subjects who received at least one dose of study drug.

Per Protocol Analysis Set

The Per-Protocol (PP) analysis set is a subset of the FAS and includes all FAS subjects who meet all of the following criteria that could impact the key objectives of the study:

- Measurable disease per RECIST 1.1 and IERC assessment
- Distant metastatic disease
- No prior anti-cancer therapy for metastatic disease
- No prior therapy with any antibody/drug targeting T-cell coregulatory proteins such as anti-PD-1, CCI, or anticytotoxic T-lymphocyte antigen-4 (CTLA-4) antibody
- Histologically proven MCC with confirmation of the diagnosis by immuno-histochemistry detection of CK20 (or other appropriate cytokeratin expression such as pancytokeratin, AE1/AE3, or Cam5.2) according to the assessment documented in the “Disease History” eCRF page.
- No active central nervous system (CNS) metastases; subjects with a history of treated CNS metastases (by surgery or radiation therapy) must have fully recovered from treatment, demonstrated no progression for at least 2 months, and not require continued steroid therapy.

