14.2 Subsequent Anti-Cancer Therapies/Procedures

Subsequent anti-cancer treatment will be provided in a data listing with data retrieved from “Anti-Cancer Treatment after Discontinuation Details”, “Radiotherapy after Discontinuation”, and “Surgery after Discontinuation” eCRF pages. The earliest date of start of new anti-cancer *drug* therapy will be used for the definition of the on-treatment period; the earliest date of start of any new anti-cancer therapy will be used for censoring for efficacy analyses.

15 Treatment Compliance and Exposure

Analysis sets: FAS / Safety analysis set

All dosing calculations and summaries will be based on “Avelumab Administration Details” eCRF pages.

Subjects will receive an IV infusion of avelumab at a dose of 10 mg/kg (over the duration of 1 hour [-10 minutes / +20 minutes, that is, over 50 to 80 minutes]) once every 2 weeks (one cycle). Analysis of exposure will be based on the calculated actual dose levels (total dose administered/weight, mg/kg). The last available weight of the subject within 3 days prior to the day of dosing will be used.

In case of missing total dose, the dose level as entered in the eCRF will be used.

The duration of therapy (in weeks) during the study is defined as:

$$\text{duration} = \left(\frac{\text{date of last dose} - \text{date of first dose} + 14}{7} \right)$$

The cumulative dose (mg/kg) per subject in a time period is the sum of the actual dose levels that the subject received within that period (i.e. total dose administered (mg) / weight (kg)).

Each cycle is defined by a 2-week period. The dose intensity and the relative dose intensity will be calculated for each subject across all cycles. The dose intensity (mg/kg/cycle) per cycle is defined as

$$\text{dose intensity} = \left(\frac{\text{Cumulative dose}}{(\text{duration of therapy (in weeks)})/2} \right)$$

The relative dose intensity is defined as the actual dose intensity divided by the planned dose per cycle.

The summary of treatment exposure and compliance table will include the following information:

- Duration of therapy (weeks)
- Total number of infusions received
- Cumulative dose of therapy (mg/kg)
- Dose intensity (mg/kg/cycle)
- Relative dose intensity of therapy (%)

A listing of treatment exposure and compliance will also be created to summarize the information listed above for each subject.

Partial Doses

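### Part B SAP: local anti-cancer treatment ongoing at entry, and anti-cancer therapy given while avelumab continues, may stay in both the primary and the per-protocol DRR

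*SAP*

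**What the plan says.** **Deviation list (Part B SAP, Appendix I).** The Clinically Important column is Yes for PDEV03, 04, 07, 18 and 19. It is blank for PDEV08, which covers exclusion criterion 4 ("Concurrent anti-cancer treatment (for example, cytoreductive therapy, radiotherapy" and so on, with exemptions). It is also blank for PDEV11, headed "Non-permitted concomitant medication during the study" and described as "Subject took Immunotherapy, immunosuppressive drugs (that is, chemotherapy or systemic corticosteroids" and so on.

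**Per-protocol set (Part B SAP, Section 10).** The set "includes all FAS subjects who meet all of the following criteria that could impact the key objectives of the study". Seven criteria follow. The modification history for version 3.0 says that the definition was updated to match the clinically important deviations. None of the seven names concurrent or on-study anti-cancer treatment. The nearest requires no earlier anti-cancer therapy for metastatic disease. Protocol 8.4 describes the set as the "subset of the Safety population that is compliant with the protocol and excludes subjects with protocol violations" and leaves the violation criteria to the SAP.

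**New therapy during follow-up.** Section 16.2.2 uses only assessments before further anti-cancer treatment for best response. Section 16.2.3 applies the PFS censoring rules to duration of response, and Table 4 censors at the last adequate assessment before new therapy. Under 16.1, a censored duration below 6 months is a failure for DRR.

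**Date source (Part B SAP, 14.2).** "Subsequent anti-cancer treatment will be provided in a data listing with data retrieved from" three eCRF pages, all titled for the time after discontinuation. The same section censors efficacy at the earliest start of any new anti-cancer therapy and names no other page. Section 11 refers to 14.2 for the date of new drug therapy. Under 14.1, concurrent procedures are only listed.

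**The concern.** Part B is single-arm, and Protocol 5.1 calls it confirmatory for some approvals. A durable response is read as an effect of avelumab, so a second active treatment bears directly on that reading. The per-protocol set removes subjects for earlier checkpoint therapy and for earlier therapy of metastatic disease, but does not name treatment running alongside avelumab.

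The per-protocol analysis is also the only sensitivity analysis of DRR in Section 16.1. If a confounded response passes through both the primary and the per-protocol analysis, no planned analysis shows DRR without it.

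The protocol foresees overlap during treatment. Section 6.5.2 allows discussion with the sponsor on whether avelumab must stop after a non-permitted drug. Section 5.5.1 allows avelumab to continue after a progressing lesion is removed or irradiated. The investigator manages the subject while the IERC decides the endpoint. A subject whom the investigator considers progressed, but the IERC does not, could therefore have local treatment while the IERC response runs on.

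**Working it through.** **1. The plan's own figures.** Inputs: N = 112, assumed DRR 45%, and the historical 11/62 (Part B SAP, Section 7). The Clopper-Pearson limits are L = Beta quantile (0.025; x, n−x+1) and U = Beta quantile (0.975; x+1, n−x).

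- 32/112: 20.4 to 37.9. 45/112: 31.0 to 49.9. 50/112: 35.2 to 54.3. 11/62: 9.2 to 29.5. All match the SAP.
- The smallest counts with L above 20% and 30% are 32 and 44. At 45%, P(X ≥ 32) = 99.99% and P(X ≥ 44) = 90.6%, in line with the stated >99% and 90%.
- 44 is also the smallest count with L above 29.5%.

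**2. Which cases the rules reach.**

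| Case | Applicable text | Kept out of primary DRR? | Kept out of PP DRR? |
|---|---|---|---|
| New therapy, date captured | 16.1, 16.2.2, 16.2.3, Table 4 | Yes, if response is first seen or confirmed only afterwards, or duration is cut below 6 months | Same |
| Systemic therapy ongoing at entry | PP criterion on earlier therapy; PDEV18, PDEV07 | No | Mostly |
| Non-exempt radiotherapy or other local treatment ongoing at entry | PDEV08, blank | No | Not clearly |
| Therapy while avelumab continues | 14.2 names no page for it | Not assured | Not assured |

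Treatment ongoing at entry is neither new nor further therapy, so the censoring rules do not reach it. Protocol 6.5.1 drops all assessments after a skin target lesion is irradiated. The Part B SAP does not repeat that rule, and it covers no other lesion.

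**3. Illustrative size.** The documents give no number of affected subjects. Assume that k of the 45 durable responders in the SAP's 45/112 example are affected.

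| k | As failures: (45−k)/112 | Lower limit | Excluded: (45−k)/(112−k) | Lower limit | PP share if no other exclusions |
|---|---|---|---|---|---|
| 1 | 39.3% | 30.2% | 39.6% | 30.5% | 99.1% |
| 2 | 38.4% | 29.4% | 39.1% | 29.9% | 98.2% |
| 3 | 37.5% | 28.5% | 38.5% | 29.4% | 97.3% |
| 5 | 35.7% | 26.9% | 37.4% | 28.2% | 95.5% |
| 6 | 34.8% | 26.1% | 36.8% | 27.6% | 94.6% |

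The failure columns correspond to the date-source fix, which censors duration before the therapy, when that leaves less than 6 months. The exclusion columns correspond to the PP fix.

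**4. The 95% rule.** 0.95 × 112 = 106.4. With 107 or more subjects in the PP set, the PP analysis is omitted, so at least 6 must be excluded for any reason.

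**5. A higher starting point.** From 50/112, six recoded failures leave 44/112 (lower limit 30.2%). A seventh gives 43/112 (29.4%).

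**The case against.** The strongest reply is that the plan already deals with most of this, and much of that reply stands.

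- A reader might infer from the blank PDEV08 and PDEV11 cells that any response confounded by another therapy stays in both analyses. The documents do not support that. Captured new therapy blocks or censors the response in the FAS and the PP set alike.
- Treatment ongoing at entry in a subject already metastatic can be read as earlier therapy for metastatic disease, and Section 13.3.2 collects prior therapy on drug, radiotherapy and surgery pages. This reading covers systemic cases well. It is less secure for local treatment: the matching deviation, PDEV18, concerns systemic treatment only, and the PP list was built to match the deviations.
- A reader might take "or may influence the efficacy evaluation of the investigational agent" (Protocol 5.3.2) as the reason for all of exclusion criterion 4. In the text it qualifies only radiotherapy to superficial lesions.
- Section 14.2 can be read as naming the three pages for a listing only, with the censoring date unrestricted. That is possible, but no other source is named, so a programmer would have to guess.
- A reader might expect 42/109 to appear as a PP result. It would not appear on its own: 109/112 = 97.3%, above the 95% cut-off. The 29.5% limit is also part of a precision illustration, not a decision rule.
- PDEV11 includes corticosteroids and other immunosuppressants, so only its anti-cancer part matters here. Important deviations are in any case listed and summarised, so affected subjects can be found.

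**Conclusion.** The point holds in a narrow form. Two kinds of case can remain in both the FAS and the PP DRR as the Part B SAP is written: non-exempt radiotherapy or other local treatment ongoing at entry, and anti-cancer therapy given while avelumab continues and recorded outside the three post-discontinuation pages. For the second, the censoring rule itself is sound and the gap is the source of the date.

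The size is unknown. From 45/112, two durable responders recoded as failures, or three excluded, bring the lower limit to 29.4%, just below 29.5%. Two excluded leave it at 29.9%. From 50/112 it would take seven recoded failures. These figures assume that every affected subject is a durable responder and, for recoding, that duration before the other therapy is below 6 months. This is a low-cost improvement that should be made, not a flaw that undermines the primary analysis.

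**What to change.** 1. In Appendix I, mark PDEV08 as clinically important. In Section 10, add a PP criterion of no concurrent anti-cancer treatment at entry (exclusion criterion 4).
2. In 14.2, 16.2.2 and Table 4, define the new-therapy date as the earliest start of any non-permitted anti-cancer treatment after the first dose, from any eCRF page, including concomitant medications and procedures. Leave out corticosteroids and the radiotherapy that Protocol 6.5.2 exempts. State explicitly how local treatment under Protocol 5.5.1 is counted.
3. Carry the Protocol 6.5.1 rule on irradiated skin target lesions into the Part B SAP.

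Do not make PDEV11 a PP exclusion. Censoring at the start date keeps these subjects in the denominator, whereas exclusion would remove failures.

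The cost is one table cell, one PP criterion and a few sentences, using data already collected. DRR and the PP set may become slightly smaller. Because the PP analysis may still be omitted under the 95% rule, the second change does more for the primary result than the first.

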5.1.4.2 Adverse Drug Reactions Requiring Treatment Discontinuation or Modifications

The following ADRs require permanent treatment discontinuation of avelumab:

Any Grade 4 ADRs require treatment discontinuation with avelumab except for single laboratory values out of normal range that are unlikely related to trial treatment as assessed by the Investigator, do not have any clinical correlate, and resolve within 7 days with adequate medical management.

Any Grade 3 ADRs require treatment discontinuation with avelumab except for any of the following:

- Transient (≤ 6 hours) Grade 3 flu-like symptoms or fever, which is controlled with medical management
- Transient (≤ 24 hours) Grade 3 fatigue, local reactions, headache, nausea, emesis that resolves to Grade ≤ 1

- Single laboratory values out of normal range (excluding Grade ≥ 3 liver function test increase) that are unlikely related to trial treatment according to the Investigator, do not have any clinical correlate, and resolve to Grade ≤ 1 within 7 days with adequate medical management
- Tumor flare phenomenon defined as local pain, irritation, or rash localized at sites of known or suspected tumor
- Change in Eastern Cooperative Oncology Group Performance Status (ECOG PS) to ≥ 3 that does not resolve to ≤ 2 within 14 days (infusions should not be given on the following cycle, if the ECOG PS is ≥ 3 on the day of study drug administration)
- Asymptomatic Grade ≥ 3 lipase or amylase elevation not associated with clinical manifestations of pancreatitis. Medical Monitor must be consulted for such lipase and amylase abnormalities.

Any Grade 2 ADR should be managed as follows:

- Infusion should not be given in case of ongoing Grade 2 ADR on the day of study treatment administration.
- Treatment can be resumed according to the original schedule once the ADR has resolved to Grade ≤ 1 . Up to 2 subsequent study drug may be omitted. If more than 2 doses are skipped, treatment may be resumed after consultation with the Medical Monitor.

Infusion-related reactions, hypersensitivity reactions (Grades 1 to 4), tumor lysis syndrome, and irAEs should be handled according to guidelines in Sections 6.5.4.1, 6.5.4.2, 6.5.4.3, and 6.5.4.4, respectively.

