6.12 Treatment of Overdose

An overdose is defined as any dose $\geq 10\%$ than the calculated dose for that particular administration. Any overdose must be recorded in the study drug section of the eCRF.

For monitoring purposes, any case of overdose, whether or not associated with an AE (serious or nonserious), must be reported to the Sponsor's Global Drug Safety department in an expedited manner using the appropriate reporting form (see Section 7.4.1.4).

There are no known symptoms of avelumab overdose to date. The Investigator should use his or her clinical judgment when treating an overdose of the study drug.

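### Part B's PDEV16 dosing-error check uses whole-course relative dose intensity, so it can list correctly dosed subjects with delays and miss single wrong doses

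*SAP*

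**What the plan says.** Row PDEV16 in Part B SAP Appendix I is headed "Subjects dosing error", with a tolerance of 10% either side of the assigned dose. It refers to Protocol Section 6.2, where the dose is worked out from body weight for each administration. The check column reads "List if relative dose intensity", with limits of at least 1.10 or at most 0.90. The row has no medical-review entry, which most rows have, and is not marked clinically important.

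Part B SAP Section 15 fixes what RDI means: "The dose intensity and the relative dose intensity will be calculated for each subject across all cycles", and "The relative dose intensity is defined as the actual dose intensity divided by the planned dose per cycle". Dose intensity is cumulative dose divided by the number of 2-week cycles. The number of cycles comes from elapsed time: last dose date minus first dose date, plus 14 days.

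Three other places bear on the point:
- Protocol 6.12 sets a 10% threshold for overdose, judged against the calculated dose of one infusion ("than the calculated dose for that particular administration"). A word seems to be missing there; I read it as 10% or more above.
- Protocol 5.1.4.2 says of Grade 2 adverse drug reactions: "Up to 2 subsequent study drug may be omitted". Protocol 6.5.3 lets treatment be delayed by up to 4 weeks for surgery not directed at a tumor lesion.
- Part B SAP 12.2 counts an incorrect dose as an important deviation, but excepts a lower dose that results from an interruption for an adverse event at the infusion.

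**The concern.** The label describes a property of one infusion. The check measures a property of the whole course. Two errors follow. A late dose lengthens the denominator, so a subject who received the right amount every time can be listed as a dosing error. One wrong dose is spread over all infusions, so it can fall inside the limits. RDI also cannot apply the Section 12.2 exception, because it does not know why the total was low. At stake is whether the PDEV16 entries in the important-deviation outputs mean what their label says.

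**Working it through.** **Inputs.** Planned dose 10 mg/kg per 14-day cycle and the RDI formula (Part B SAP Section 15); limits 0.90 and 1.10 (Appendix I, PDEV16); overdose threshold 10% per administration (Protocol 6.12). The plan gives no worked figure to reproduce. As a check on the formula, 7 full on-time doses run from day 1 to day 85. Duration is (84 + 14)/7 = 14 weeks, or 7 cycles. Dose intensity is 70/7 = 10, and RDI is 10/10 = 1.00, as it should be.

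**Delays, every dose correct.** With n infusions and D days of total delay between first and last dose, the course spans n + D/14 cycles, so

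RDI = n / (n + D/14).

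The subject is listed when this is 0.90 or less, that is, when D/14 ≥ n/9.

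| Total delay | RDI at selected n | Listed for |
|---|---|---|
| 3 days | 0.903 (n=2) | never |
| 7 days | 0.889 (n=4), 0.909 (n=5) | n = 2 to 4 |
| 14 days | 0.875 (n=7), 0.900 (n=9), 0.909 (n=10) | n = 2 to 9 |
| 28 days | 0.833 (n=10), 0.900 (n=18), 0.905 (n=19) | n = 2 to 18 |

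One omitted dose adds 14 days and two add 28, so the last two rows correspond to omissions that Protocol 5.1.4.2 foresees. The last row also matches the 4-week maximum in Protocol 6.5.3.

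**One wrong dose, all doses on time.** If one of n doses is f times the planned dose,

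RDI = 1 + (f − 1)/n.

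An overdose is listed when n ≤ 10(f − 1).

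| Single dose | RDI at selected n | Listed for |
|---|---|---|
| 1.1 × planned | 1.050 (n=2), 1.014 (n=7) | n = 1 only |
| 1.2 × planned | 1.100 (n=2), 1.067 (n=3) | n ≤ 2 |
| 1.5 × planned | 1.100 (n=5), 1.071 (n=7) | n ≤ 5 |
| 2.0 × planned | 1.100 (n=10), 1.077 (n=13) | n ≤ 10 |

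In a 12-infusion course, one dose must reach 1 + 0.10 × 12 = 2.2 times plan before it is listed.

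**Mixed cases.**
- One 50% overdose and one 14-day delay in 7 infusions: (15 + 60)/(8 × 10) = 0.9375. The two effects offset each other and nothing is listed.
- One half dose, the rest full: 1 − 0.5/n, listed for n ≤ 5 (0.90 at n=5). If an adverse event cut that dose short, Section 12.2 excepts it, yet the check lists it.
- Two full doses, the second 3 days early, which the visit window in Protocol 7.1.2 allows: 2/(25/14) = 1.12, listed on the high side.

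**Same cases per infusion.** Actual over planned mg/kg is 1.00 for any full dose, however late or early, and 1.10 for a 10% overdose, whatever the course length.

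**The case against.** The mismatch is hard to dispute, but several limits stand.

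- A reader might infer that overdoses would go unreported. The documents do not support that. Protocol 6.12 requires every overdose to be recorded in the eCRF and sent to drug safety on an expedited basis. Part B SAP 12.2 lets deviations be found by site monitoring, medical review or programming. PDEV99 covers other significant deviations, and Section 15 provides a listing of every administration. Only the programmed PDEV16 line misses them.
- Low doses and delays are already visible elsewhere. Section 15 counts doses below 90% of plan per administration and tabulates delays in six categories. It has no matching summary of doses above plan.
- A reader might infer that any permitted delay is listed. It is not: total delay must reach about 11% of the on-schedule course (D/14 ≥ n/9).
- A delayed subject is not automatically compliant. Protocol 6.9 treats missing more than one cycle for nonmedical reasons as noncompliance, so the false-listing argument applies only where the delay had a permitted reason.

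All four points stand. They limit the consequence; they do not make RDI a valid test of a per-dose label.

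**Conclusion.** The PDEV16 check does not test what PDEV16 names. Followed as written, it lists correctly dosed subjects after 14 days of delay in courses of up to 9 infusions and after 28 days in courses of up to 18. It catches a single 10% overdose only when there was one infusion. These ranges assume a single dose departure or delay in an otherwise perfect course; mixed courses can move either way. The share of Part B subjects affected depends on course lengths and delays that the documents do not give.

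It would be tempting to read this as a threat to the efficacy analysis, but the documents do not support that. No per-protocol criterion in Part B SAP Section 10 concerns dose, so the per-protocol set, the full analysis set and the durable response rate with its interval are unchanged. The effect stays within the programmed PDEV16 listing and summary. Severity: minor.

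**What to change.** In Appendix I, replace the RDI condition in PDEV16 with a per-administration one: list any infusion whose actual mg/kg divided by planned mg/kg is at least 1.10 or at most 0.90. Settle the lower boundary with Section 15, where a partial dose is strictly below 90% of plan; as it stands, a dose of exactly 90% meets one definition and not the other. Add medical review to the row, so that the Section 12.2 exception for a dose cut short by an adverse event can be applied case by case. Leave RDI in Section 15 as an exposure summary.

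The cost is a small amount of programming on administration data that the eCRF already collects, plus review of the low doses to decide which are excepted. No new data and no change to any clinical rule are needed.
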